- If a patient develops hypoglycemia (BG <70 mg/dL), the insulin TDD (basal and prandial) should be decreased by 20%.
- If a patient develops severe hypoglycemia (BG <40 mg/dL), the insulin TDD (basal and prandial) should be decreased by 30-40%.

IV.g. Data Analysis:

Aim 1. To determine differences in inpatient glycemic control, as measured by mean daily blood glucose concentration and frequency of hypoglycemia, in general medicine and surgery patients with T2D treated with basal bolus regimen with glargine U300 and U100 plus glulisine insulin before meals.

Due to the lack of efficacy and safety data with the use of glargine U300 in the inpatient setting, periodic conduct interim analyses will be conducted every 6 months to monitor the primary outcome and rate of hypoglycemia, and to modify the study design regarding interval of administration and dosage adjustment for basal insulin (see page 9, Data Safety Monitoring Plan, sections IV. f. and IV.g.).

Sample Size and Power Calculations:

The primary endpoint in this study is glycemic control measured by mean daily BG concentration. To show the non-inferiority of glargine U300 and U100 in terms of glycemic control, we set the equivalence margin as 18 mg/dl (1 mosm/l), from a view that a difference <18 mg/dl is usually not considered as clinically significant (12, 14, 16). Based on the results from Rabbit medicine and surgery trials, it is reasonable to assume the standard deviation of mean daily BG is bounded above by 45 mg/dl. Assuming the true BG difference between the treatment groups is zero, and using one-sided, two-sample t-tests, we require 78 subjects for each treatment group to achieve 80% power. Accounting for 10% attrition rate, we would need 90 patients per treatment group, which means 180 subjects in total, to achieve >80% power in Aim 1.

Analysis of Primary Endpoint:

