V. Aim 2: To determine differences in glycemic control after hospital discharge between treatment with glargine U300 and glargine U100 in medicine and surgery patients T2D.

[figure not shown]
V.a. Rationale. Few studies have addressed the efficacy of insulin alone or in combination with oral agents after hospital discharge. In a recent study (see preliminary results section), patients were discharged on a combination of OADs and glargine U100 insulin or on a basal bolus regimen according to bA1c levels and achieved a marked reduction in HbA1c from 8.75% on admission to 7.9% and 7.35% after 4 and 12 weeks of hospital discharge. However, the use of glargine U100 alone or in combination to oral agents or as basal bolus insulin resulted in 30% and close to 40% incidence of hypoglycemia, respectively. In this study, we will compare the efficacy and safety of glargine U300 and U100 after hospital discharge. The total duration of the study is 3 months. Several outpatient insulin trials have shown that treatment with glargine U300 results in similar improvement in glycemic control, but in significant reduction in hypoglycemia compared to glargine U100 (23-27). Thus we expect that glargine U300 will be a safer alternative to current use of glargine U100 formulation.

V.b Insulin Discharge algorithm:

Patients with poorly controlled diabetes ($HbA1c \geq 7.5\%$) enrolled in Aim 1 will be invited to participate in this open label prospective outpatient study. The total duration of the study is 3 months.

- Patients with admission Hba1c < 7.5% will be discharged on their preadmission antidiabetic regimen and will not be included in the Aim 2 outpatient study.
- Patients with no previous pharmacological treatment prior to admission will be discharged on 50% of daily basal insulin (glargine U300 or glargine U100) hospital dose.
- Patients on oral agents prior to admission with an HbA1c between 7.5% and <10% will be discharged on oral agents plus glargine U300 or glargine U100 at 50% of the daily hospital dose.
- Patients on oral agents prior to admission with an admission A1C ≥ 10% will be discharged on their oral agents plus glargine U300 or glargine U100 at 80% of daily hospital dose. If previous basal bolus only therapy or contraindications to previous oral therapy, discharge on basal bolus at 100% of daily hospital dose.

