If any FBG or RBG 40- 69 mg/dl	Decrease by 8 IU or 20% of total daily dose
If any FBG or RBG < 40 mg/dl	Decrease total daily dose by 30 - 40%

V.g. Aim 2. Statistical Analysis:

V.g.1. Sample Size and Power Calculations: The primary endpoint in Aim 2 is difference in glycemic control (mean daily BG) after hospital discharge. Under the same assumptions for equivalence margin and BG variability as in Aim 1, we have the same sample size requirement (i.e. 78 subjects per group after 10% attrition). Accounting for 10% attrition rate, we would need 90 patients per treatment group (total # of patients to be recruited: 180 subjects, 90 per treatment group), to achieve >80% power.

V.g.2. Analysis of Primary Endpoint:

The primary endpoint in this study is glycemic control measured by mean daily BG concentration after hospital discharge. Secondary outcomes include rate of hypoglycemia during follow-up, change in HbA1c, body weight in kilograms, number of episodes of severe hyperglycemia, complications and emergency room visits or hospital readmissions at 12 weeks post-discharge. To analyze these outcomes, we will follow the same analytic strategy proposed for the secondary endpoints of Aim 1. We will first compare the primary outcome using two-sample t-tests (or Wilcoxon tests) or one-way ANOVA, followed by multivariate linear regression to estimate and test the difference between the two treatment groups while simultaneously accounting for other potential confounders. Transformations will be applied if normality violation is detected. Stepwise, backward, or forward model selection strategy will be adopted to determine the variables to be included in the final model. Standard diagnostic and model checking procedures will be applied to examine the fit of the developed models.

DATA HANDLING AND RECORD KEEPING:

Data collection records with personal identifiers will be stored in locked file cabinets. Presentation of the study results at regional or scientific meetings or in publications will not identify subjects. Access to research and confidential records will be limited to clinical investigators, research coordinators, and the IRB at Emory University.

All data will be entered electronically in Redcap by participating sites. Sponsor site expects data to be entered in Redcap within 10 days of phone call or outpatient visit.

VI. Methods and Procedures Applied to Human Subjects:

VI.a. Subject Population:

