We plan to study a total of 180 randomized patients with a known history of T2D, age > 18 years, treated with diet alone, any combination of oral antidiabetic agents, GLP1-RA (except long-acting agents: albiglutide, albiglutide and weekly exenatide) or insulin therapy (except degludec or glargine U300). Patients included within this study will be determined by the set of inclusion and exclusion criteria.

VI.b. Inclusion Criteria:

1. Males or females between > 18 years admitted to a general medicine or surgical service.
2. Known histories of T2D treated with either diet alone, oral monotherapy, any combination of oral antidiabetic agents, short-acting GLP1-RA (exenatide, liraglutide) or insulin therapy with the exception of degludec and glargine U300.
3. Subjects must have a randomization BG > 140 mg and < 400 mg/dL without laboratory evidence of diabetic ketoacidosis (bicarbonate < 18 mEq/L, pH < 7.30, or positive serum or urinary ketones).

VI.c. Exclusion Criteria:

1. Subjects with increased BG concentration, but without a known history of diabetes.
2. Admission or pre-randomization BG ≥ 400 mg/dl
3. Patients treated with degludec or glargine U300, or with long-acting weekly GLP1-RA (weekly exenatide, dulaglutide or albiglutide).
4. Patients with acute critical or surgical illness admitted to the ICU or expected to require admission to the ICU.
5. Patients with clinically relevant hepatic disease (diagnosed liver cirrhosis and portal hypertension), corticosteroid therapy, or impaired renal function (eGFR < 30 ml/min).
6. Mental condition rendering the subject unable to understand the nature, scope, and possible consequences of the study.
7. Female subjects who are pregnant or breast-feeding at time of enrollment into the study.

VI.d. Withdrawal Criteria

1. The subject may withdraw at will at any time.
2. The subject may be withdrawn from the trial at the discretion of the investigator due to a safety concern or if judged non-compliant with trial procedures or included in contravention to the inclusion and/or exclusion criteria.
3. Subject admitted to the ICU who required continuous intravenous insulin infusion to maintain glycemic control.
4. Pregnancy or intention to become pregnant.
5. Treatment with oral or injectable corticosteroid (equivalent or higher than prednisone 5mg/day), parenteral nutrition and immunosuppressive treatment after randomization.

Treatment Failure Criteria

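### Aim 2 is sized at 180 patients for >80% power, but it can draw only on the volunteers with HbA1c ≥7.5% among the 180 patients of Aim 1

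*Combined protocol and SAP*

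**What the plan says.** All references are to the combined protocol and SAP.

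- **Size of the study.** Section VI.a: "We plan to study a total of 180 randomized patients". Section IV.b gives the same total for Aim 1, from about 300 consented, and IV.d splits it 90 and 90.
- **Entry to Aim 1.** The criteria in VI.b are known type 2 diabetes and a glucose range: "Subjects must have a randomization BG > 140 mg and < 400 mg/dL without laboratory evidence of diabetic ketoacidosis". No HbA1c limit is set.
- **Entry to Aim 2.** Under V.b, patients with HbA1c of 7.5% or more "enrolled in Aim 1 will be invited to participate in this open label prospective outpatient study". Those below 7.5% "will be discharged on their preadmission antidiabetic regimen and will not be included in the Aim 2 outpatient study".
- **Aim 1 sizing (IV.g).** The margin is 18 mg/dl and the true difference zero. On the SD, "it is reasonable to assume the standard deviation of mean daily BG is bounded above by 45 mg/dl". On the number, "using one-sided, two-sample t-tests, we require 78 subjects for each treatment group to achieve 80% power". This is raised to 90 per group for 10% attrition.
- **Aim 2 sizing (V.g.1).** "Under the same assumptions for equivalence margin and BG variability as in Aim 1, we have the same sample size requirement". The result is again 78 evaluable and 90 recruited per group, given as "total # of patients to be recruited: 180 subjects, 90 per treatment group", for more than 80% power.

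**The concern.** The Aim 2 number equals the whole Aim 1 number, yet Aim 2 admits only a subset of Aim 1. The plan itself expects the subset to be smaller: it writes a discharge rule for patients below 7.5% (V.b), allows for 10% attrition in Aim 1 (IV.g) and discontinues treatment failures (Treatment Failure Criteria). It gives no expected share with HbA1c of 7.5% or more, no expected uptake, no second source of patients and no larger Aim 1.

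Aim 2 has its own primary endpoint (mean daily glucose after discharge), its own hypothesis of similar control and its own power statement. A smaller sample does not make a false non-inferiority conclusion more likely, but it does make an inconclusive interval more likely. V.g.2 plans ordinary two-sample comparisons and does not mention the margin. A non-significant difference could then be read as similarity on the strength of a stated power that the design does not deliver. Aim 1 sizing is not affected.

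**Working it through.** **Inputs.** Margin 18 mg/dl, SD 45 mg/dl, true difference 0, one-sided two-sample t-test (IV.g, carried into V.g.1); attrition 10% (V.g.1); 90 per group randomised (IV.d). Alpha is not stated. One-sided 0.05 is inferred because it reproduces the plan's 78; one-sided 0.025 would need 100 per group.

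**Formula.** Power for *n* per group is P(T > t₀.₉₅,₂ₙ₋₂), where T is noncentral t with 2n − 2 degrees of freedom and noncentrality 18 / (SD × √(2/n)).

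**1. The plan's own figures.** For n = 78: 45 × √(2/78) = 7.206, noncentrality 18/7.206 = 2.498, power 0.8001. For n = 77, power is 0.796. So 78 is the smallest adequate number and reproduces exactly. With 90 recruited, 90 × 0.9 = 81 are evaluable and power is 0.813. The formula has been applied correctly; the question is whether 90 per group can exist in Aim 2.

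**2. Entry share needed.** Let *f* be the share of Aim 1 patients who enter Aim 2. Evaluable per group = 90 × f × 0.9 = 81f. Setting 81f = 78 gives f = 78/81 = 156/162 = 96.3%.

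**3. Plan values only, with no HbA1c assumption.** If the 10% lost in Aim 1 cannot enter Aim 2, and Aim 2 then loses its own 10%, 90 × 0.9 × 0.9 = 72.9, so 72 per group. Power at SD 45 is 0.771, even if every remaining patient is eligible and accepts.

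**4. Illustrative entry shares.** The documents give no value for *f*; the shares below are assumptions. n = 90 × f × 0.9, rounded down. The half-width of the 90% confidence interval is t₀.₉₅,₂ₙ₋₂ × 45 × √(2/n).

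| Assumed f | n per group | Power, SD 45 | 90% CI half-width, SD 45 (mg/dl) | Power, SD 32 | Largest SD giving 80% power (mg/dl) |
|---|---|---|---|---|---|
| 80% | 64 | 0.728 | 13.2 | 0.936 | 40.7 |
| 60% | 48 | 0.618 | 15.3 | 0.862 | 35.2 |
| 50% | 40 | 0.551 | 16.7 | 0.802 | 32.1 |

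Worked row, f = 50%: 45 × √(2/40) = 10.062; noncentrality 18/10.062 = 1.789; power 0.551; half-width 1.6646 × 10.062 = 16.7.

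SD 32 is the inpatient basal-bolus figure from the surgery trial in section III. It is shown for sensitivity; V.g.1 does not use it.

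**The case against.** **The power loss is possible rather than shown.** The entry share is unknown, and 45 mg/dl is described as an upper bound. At SD 32, even 40 per group reaches 80%. This stands as a limit on the size of the harm. But 32 is an inpatient surgical figure, V.g.1 expressly adopts the Aim 1 variability, and no post-discharge SD is justified. A smaller SD could rescue the power; it cannot make 180 recruits available.

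**V.g.1 states what would be needed, not what will happen.** The sentence is conditional, but its parenthesis gives a number to be recruited. A requirement that the design cannot be expected to meet still leaves the power claim unsupported.

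**There may be another pool.** About 300 are to be consented, but only 180 are randomised, and Aim 2 compares the randomised groups. The Aim 2 flow chart has consent and randomisation rows, but both are at Hospital Day 1. Neither supplies extra patients.

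**Aim 2 is a follow-on.** The study's main outcome is inpatient glucose, and a smaller Aim 2 costs precision without adding bias. That is fair. The lack of a margin in V.g.2 is also a separate matter that would remain at full enrolment. Neither point makes the stated number right.

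**Conclusion.** The concern holds. V.g.1 gives Aim 2 a sample size, and a power resting on it, that the design does not supply. This is an inconsistency between the sample size and the source of patients, not a slip in the formula.

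At SD 45 and an inferred one-sided alpha of 0.05, 80% power requires about 96% of Aim 1 patients to enter. The plan's own attrition applied in both phases gives 77% at best. At assumed entry shares of 80% down to 50%, power runs from 73% to 55%. Those last figures depend on the assumed shares and on SD 45; the inconsistency depends on neither. A stricter alpha would lower every power figure: at one-sided 0.025, 81 evaluable per group gives 0.716.

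**What to change.** In V.g.1, replace the recruitment figure of 180 and the claim of more than 80% power with:

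1. the expected number of Aim 1 patients who will have HbA1c of 7.5% or more and accept, net of Aim 1 losses, with the basis for that expectation;
2. the alpha level;
3. a justified SD for post-discharge mean daily glucose;
4. the power, or the expected confidence interval half-width, that follows.

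If the power is below 80%, say so, and commit to reporting the Aim 2 difference with its confidence interval against the 18 mg/dl margin.

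The cost is a few sentences in V.g.1 and a line in V.g.2 for the interval. No extra enrolment is needed and Aim 1 is untouched. The drawback is that the stated Aim 2 power may look less favourable. If the sponsor prefers to keep 180 in Aim 2, Aim 1 would have to randomise 180/f before any allowance for Aim 1 losses: 225 at an 80% share, 300 at 60%, 360 at 50%. Labelling Aim 2 exploratory is the other option. That choice belongs to the sponsor.

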Hypothesis: Treatment with glargine U300 will result in equivalent glycemic control in hospitalized patients with T2D. Glargine U300 will result in lower number of hypoglycemia compared to glargine.

Aim 2: To determine differences in glycemic control after hospital discharge between treatment with glargine U300 and glargine U100 in medicine and surgery patients T2D. Patients with poorly controlled diabetes ($HbA1c \geq 7.5\%$) enrolled in Aim 1 will be invited to participate in this open label prospective outpatient study. The total duration of the study is 3 months. Patients with an $HbA1c$ between 7.5% and 10% will be discharged on preadmission oral antidiabetic agents plus glargine U300 and U100 once daily. Patients with an admission $A1C \geq 10\%$ will be discharged on basal bolus regimen with glargine and glulisine insulin before meals.

Hypothesis: treatment with glargine U300 and U100 will result in a similar improvement in HbA1c levels after hospital discharge. Glargine U300 will result in lower number of hypoglycemia compared to U100.

II. BACKGROUND AND CURRENT STATUS OF WORK IN THE FIELD.

Inpatient glycemic control in non-ICU setting. A large body of evidence has shown that in hospitalized patients, the presence of hyperglycemia and diabetes is associated with increased risk of complications and death (1-6, 28-31). Several randomized multi-center trials have shown that the use of basal bolus insulin regimen result in improved glycemic control and reduced rate of hospital complications compared to sliding scale regular insulin (SSI) in patients with T2D (12-14). We have reported that treatment with basal and basal bolus regimens using glargine U100 results in greater improvement in BG control and a reduction in the frequency of hospital complications including postoperative wound infection, pneumonia, bacteremia, and acute renal and respiratory failure compared to SSI treatment.(16, 17, 32, 33) In addition, the use of basal bolus regimen with glargine U100 is safe with low rate of hypoglycemic events. Based on these studies and others, clinical practice guidelines for the management of hyperglycemia in non-ICU setting have favored the use of basal prandial insulin regimens with insulin analogs for most inpatients with T2D (6, 19, 31).

Efficacy and safety of new glargine U-300 insulin:

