In the Rabbit-Surgery trial (Figure 2), 211 general non-cardiac surgery patients with T2D were randomized to a basal bolus (BB) with glargine once daily and glulisine before meals and to sliding scale regular insulin (SSI). Study outcomes included differences in daily BG levels and a composite of hospital complications including postoperative wound infection, pneumonia, respiratory failure, acute renal failure, and bacteremia. The mean daily glucose after the 1st day of BB and SSI was 145±32 mg/dl and 172±47 mg/dl, respectively, p<0.01. BG readings <140 mg/dl were recorded in 55% of patients in BB and 31% in the SSI group, p<0.001. There were reductions with BB as compared with SSI in the composite outcome (24.3% and 8.6%, OR: 3.39 (95% CI: 1.50-7.65); p=0.003). We concluded that treatment with BB improved glycemic control and reduced complications compared to SSI in surgery patients with T2D.

Basal insulin during Hospital Discharge.(36)

Fig 1

Mean Blood Glucose Levels During Basal Bolus and SSRI

[figure not shown]

Figure 3. Postoperative Complications

[figure not shown]
[figure not shown]
[figure not shown]

Fig 3. Discharge Insulin Algorithm
* Composite of pneumonia, respiratory failure, acute renal failure, and bacteremia.

In a recent preliminary study we assessed the efficacy of an HbA_{1c} based algorithm for the management of non-ICU insulin treated patients with T2D (Fig. 4). A total of 214 general medicine and surgery patients with an admission HbA_{1c} < 7% were discharged on their same outpatient antidiabetic regimen (oral antidiabetic drugs, OAD and/or insulin). Patients with an HbA_{1c} between 7% and 9% were discharged on a combination of OADs and basal (glargine) insulin at 50% of total daily hospital dose. Patients with an admission HbA_{1c} ≥ 9% were discharged on a combination of oral agents and basal insulin at 80-100% of total daily hospital dose or on a basal bolus regimen at the same hospital dosage. The admission HbA_{1c} of 8.75% decreased to 7.9% and 7.35% after 4 and 12 weeks of hospital discharge respectively (p<0.01, Fig 5). Patients with higher HbA_{1c} levels experienced a greater reduction as well as those treated with basal bolus insulin regimens. We concluded that the admission HbA_{1c} concentration is beneficial in designing the discharge treatment algorithm after discharge in non-ICU patients with T2D.

Change in HbA_{1c} levels after discharge

Umperiez et al. ADA Scientific Meeting, Philadelphia 2012

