events, number of severe hyperglycemia, mean daily fasting BG, daily insulin dose, length of hospital stay, acute renal failure and hospital mortality. Blood glucose will be measured before each meal and at bedtime. For discrete outcomes (such as hypoglycemia outcomes), if the outcome is binary (e.g. with or without hypoglycemia), we will first conduct nonparametric comparisons based on a two-sided Chi-square test (or Fisher's exact test in the presence of low incidence rates), followed by the Cochran-Mantel-Haenszel test, which adjusts for the potential center effect. If the discrete outcome is a count outcome (such as the number of hypoglycemic event), we will perform Poisson regression (or Negative Binomial regression) that adjusts for the length of hospital stay to assess the difference in the count outcome between the treatment groups. We also value the repeated measures analyses based on mixed effect models. This is because they will allow us to assess treatment effect fine tuned according to other confounders of the BG outcomes. By these considerations, we will conduct both types of analyses to provide a thorough evaluation of the hypothesis of interest. For continuous outcomes that are not repeated measures (such as length of hospital stay), we will use two-sample t-tests or nonparametric Wilcoxon tests to compare them between groups. Transformations will be applied if normality violation is detected. Multivariate linear regression will be further conducted to assess the difference in continuous secondary outcomes between the two groups while other relevant covariates. We will use standard model selection and model checking procedures for linear regression to decide the final models and assess their fits to the data.

IV.f. Data and Safety Monitoring Board (DSMB):

The Data and Safety Monitoring Board (DSMB) will review unblended data on safety, treatment compliance, and evaluate the efficacy of the intervention being studied in this clinical trial. The DSMB will meet at 6-month intervals and report on study progress to the IRB.

IV.g. Interim Analysis and Stopping Rules: We plan to perform one interim analysis on the primary endpoint every 6 months and when half of the subjects have been randomized. The trial will be stopped if there is evidence beyond a reasonable doubt of a difference in the rate of death and hospital complications (two-sided alpha level, <0.01) between the treatment groups.

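### Aim 2 change in HbA1c: admission HbA1c is not a fixed covariate and no principal analysis is named, so the precision of the result is left to an unadjusted test or to data-driven model selection

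*Combined protocol and SAP*

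**What the plan says.** The Aim 2 hypothesis in I.B is stated in terms of HbA1c: "treatment with glargine U300 and U100 will result in a similar improvement in HbA1c levels after hospital discharge". V.g.2 nevertheless makes mean daily glucose the primary endpoint ("The primary endpoint in this study is glycemic control measured by mean daily BG concentration after hospital discharge") and places change in HbA1c among the secondary outcomes ("Secondary outcomes include rate of hypoglycemia during follow-up, change in HbA1c, body weight in kilograms"). For the analysis it says "we will follow the same analytic strategy proposed for the secondary endpoints of Aim 1".

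That strategy is in IV.g, Analysis of Secondary Endpoints. For continuous outcomes that are not repeated measures, "we will use two-sample t-tests or nonparametric Wilcoxon tests to compare them between groups". Then: "Multivariate linear regression will be further conducted to assess the difference in continuous secondary outcomes between the two groups while other relevant covariates". The covariates are not listed, and the final model is left to standard selection and checking procedures. V.g.2 adds, next to its text on the primary outcome, "Stepwise, backward, or forward model selection strategy will be adopted to determine the variables to be included in the final model". IV.g also expresses a preference for repeated-measures mixed models and says that both types of analysis will be done, but it discusses these in connection with glucose outcomes.

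HbA1c is measured on admission and at 1 and 3 months (V.e, VIII.a and the Aim 2 flow chart). In the preliminary discharge study (section III), patients with higher HbA1c "levels experienced a greater reduction as well as those treated with basal bolus insulin regimens".

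**The concern.** The plan's own preliminary data associate HbA1c with the later fall. Section V.b also ties the discharge regimen to admission HbA1c, with a cut at 10%. Randomisation is blocked on prior insulin use only (IV.e), so nothing in the design protects balance on HbA1c. Every Aim 2 participant must have an HbA1c value, because 7.5% or more is an entry condition. It is therefore the obvious covariate to fix in advance, and the plan does not name it.

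Two things are at stake. The first is precision. A hypothesis of similar improvement is judged by the width of a confidence interval, and Aim 2 draws only on those of the 180 randomised patients who have HbA1c of 7.5% or more and accept the invitation. The second is pre-specification. In an open-label trial the plan allows a t-test, a Wilcoxon test, a transformed analysis and several selected regressions, and does not say which gives the reported HbA1c result.

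**Working it through.** **The plan's own figure.** The only sample size stated is for mean daily glucose (IV.g, reused in V.g.1): margin 18 mg/dl, SD 45 mg/dl, true difference 0, one-sided test, 80% power, 78 per group. The alpha is not stated; one-sided 0.05 is assumed because it reproduces the figure:

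n = 2 × [45 × (1.645 + 0.842) / 18]² ≈ 77.3, so 78 per group.

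At one-sided 0.025 the result would be 99. The plan's 90 per group leaves 81 after 10% attrition (90 × 0.9). None of this concerns HbA1c, for which there is no margin, SD or power statement.

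**Precision for change in HbA1c.** Let s be the SD of HbA1c, taken as equal at baseline and follow-up, and r the correlation between the two. Up to the same factor for group size:

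- unadjusted change score: variance = 2s²(1 − r)
- adjusted for baseline (ANCOVA): variance = s²(1 − r²)
- ratio = (1 + r)/2

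The documents give no r, so a range is assumed:

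| Assumed r | Variance ratio | Reduction in standard error | n per group, adjusted, matching 78 unadjusted | Power of unadjusted test if the adjusted one has 80% |
|---|---|---|---|---|
| 0.3 | 0.65 | 19% | 51 | 64% |
| 0.5 | 0.75 | 13% | 59 | 69% |
| 0.7 | 0.85 | 8% | 67 | 74% |

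The third column is 1 − √ratio. The fourth is 78 × ratio, rounded up. The last is Φ[(1.645 + 0.842) × √ratio − 1.645]. The 78 is only a reference size here. Simulation at 78 per group gave ratios of 0.64, 0.77 and 0.85.

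**Unequal SDs.** With k = follow-up SD / baseline SD, the ratio is k²(1 − r²) / (1 + k² − 2rk). Over r = 0.3 to 0.7:

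- k = 0.75: 0.46 to 0.56
- k = 1.25: 0.78 to 0.98

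The least favourable of these cases is k = 1.25 with r = 0.7: 1.5625 × 0.51 / (2.5625 − 1.75) = 0.797 / 0.8125 = 0.98, a gain of about 2%.

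**What the documents fix.** In general the ratio is 1 − c², where c is the correlation between change and baseline. The preliminary study gives the direction (higher HbA1c, larger fall), so c is not zero there. It gives no coefficient or SD, so the size cannot be derived. Restricting Aim 2 to HbA1c of 7.5% or more narrows the baseline range and may alter it.

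**The case against.** The strongest reply is that adjustment is already planned. Regression follows the first test, and if admission HbA1c predicts the change, selection would probably keep it and recover the precision. HbA1c is also measured at two follow-up visits, so the mixed models mentioned in IV.g might be meant to apply. Both points stand. A reader might infer that the plan relies on the unadjusted test alone and so certainly loses precision; the documents do not support that. What remains is that recovery depends on an unspecified selection step, and no text says which result counts.

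Three other stronger readings are also unsupported:

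- That baseline HbA1c drives the change. Section III reports an association only, and patients with higher HbA1c in that study also received more intensive discharge regimens. An association is enough for a precision gain.
- That the change score is the least efficient choice. With equal SDs, comparing follow-up values alone has variance s², against 2s²(1 − r) for change. At r = 0.6 the change score is better (0.8s²), and at r = 0.5 the two tie.
- That the unadjusted comparison is biased. Lack of adjustment does not bias a randomised comparison; it leaves any chance imbalance uncorrected. Selection through acceptance of the Aim 2 invitation is a separate matter, which adjusting for HbA1c would not cure.

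It is also fair to say that the outcome is secondary and unpowered.

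**Conclusion.** The point holds as one of efficiency and pre-specification. The outcome in the Aim 2 efficacy hypothesis has no named principal analysis. Its apparent first test ignores a baseline value that is already collected, and the later regression does not guarantee its inclusion. Relative to an unadjusted change score, adjustment would reduce the variance by 15% to 35% for assumed correlations of 0.7 to 0.3 with equal SDs. The gain is larger if the follow-up SD is smaller than the baseline SD, and could be as little as about 2% if it is 1.25 times as large. These figures rest on assumed correlations and SD ratios. They measure the loss only if the unadjusted result is the one reported, or if selection drops admission HbA1c. The stated sample size and the Aim 2 primary endpoint are unaffected. The change is worth making before the data are analysed.

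**What to change.** Add one paragraph to V.g.2 naming the principal HbA1c analysis: a single mixed model of the 1- and 3-month HbA1c values with arm, visit, arm-by-visit interaction, admission HbA1c (continuous, with a visit-specific coefficient), prior insulin use (the randomisation stratum) and centre, and no variable selection. Report the adjusted arm difference at 3 months with its 95% confidence interval. Keep the unadjusted comparison of change as supportive only.

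Patients with only the 1-month value then contribute, under a missing-at-random assumption that the paragraph should state. A 3-month complete-case test would drop them.

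The cost is the drafting. Admission HbA1c, prior insulin use and centre are already known for every participant, and no visit, sample or patient is added.
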